9.11 Clinical Laboratory Tests

Blood and urine specimens will be collected according to the schedule specified in [Appendix 1](#). Safety laboratory tests can be performed up to 7 days prior to the infusion and must be reviewed before study drug administration.

Monitoring HIV RNA levels

In the event of HIV-1 viral load of ≥ 50 copies/mL after the infusion of MGD014, the following should occur per standard of care:

- Adherence to ART should be carefully assessed and documented.
- A standard HIV RNA assay should be repeated within 1-4 weeks.
- HIV resistance testing will be performed at the time of drawing a confirmatory sample.
- In the event of HIV-1 viremia ≥ 150 copies/mL, the participant may continue with study treatment if repeat testing is < 100 copies/mL within 4 weeks and < 50 copies/mL within 12 weeks.
- HIV RNA will be repeated every 2 weeks, or sooner as clinically indicated, until < 50 copies/mL.
- In the event of confirmed HIV-1 viremia and documented adherence to ART, ART should be managed by the primary care provider in discussion with the study team. The results of the HIV resistance tests will be shared with the participants and their care providers.

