17. Adequate vascular access for MGD014 infusion and leukapheresis.

Exception: Participants who opt out of the leukapheresis procedure, are not required to have adequate vascular access for a leukapheresis procedure.

18. Participant must have adequate organ function as indicated by the following laboratory values, at the screening visit:

Laboratory Values Required for Study Eligibility	
Test Name	Laboratory Value
Hematological	
Absolute neutrophil count	$\geq 1,500 / \mu\text{L}$
Platelets	$\geq 125,000 / \mu\text{L}$
Hemoglobin	$\geq 12 \text{ g/dL} (\text{male}) \text{ and } \geq 11 \text{ g/dL} (\text{females})$
Coagulation	
Prothrombin Time or INR	$\leq 1.1 \times \text{ULN}$
Chemistry	
K ⁺ levels	Within normal limits
Mg ⁺⁺ levels	Within normal limits
Glucose	Screening serum glucose \leq Grade 1 (fasting or non-fasting)
Albumin	$\geq 3.5 \text{ g/dL}$
Renal	
Creatinine clearance determined by the CKD-Epi equation found at: https://www.qxmd.com/calculate/calculator_251/egfr-using-ckd-epi	eGFR $> 60 \text{ mL/min}$
Hepatic	
Serum total bilirubin	Total bilirubin < 1.5 times the ULN range. If total bilirubin is elevated, direct bilirubin must be < 2 times the ULN range. NOTE: If participant is on an atazanavir-containing therapy, then a direct bilirubin should be measured instead of the total bilirubin and must be $\leq 1.0 \text{ mg/dL}$.
AST and ALT	$\leq 1.25 \times \text{ULN}$
ALK-P	$\leq 1.25 \times \text{ULN}$
Lipase	$< 1.1 \times \text{ULN}$
Serum Pregnancy	Negative

Abbreviations: ALK-P = Alkaline Phosphatase; ALT = Alanine Transaminase; AST = aspartate aminotransferase; CKD-Epi = Chronic Kidney Disease Epidemiology Collaboration; eGFR = estimated glomerular filtration rate; INR = international normalized ratio; K⁺ = potassium; Mg⁺⁺ = magnesium; ULN = upper limit of normal.

Labs/procedures completed during a routine clinical care appointment that are the same as the study screening labs and/or procedures and completed within the 14 days preceding the screening visit can be used to qualify the participant upon approval by the study PI or designee.

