5.3 Guidelines for Discontinuation of Participants from Study Drug Administration

Under certain circumstances, an individual participant's infusions will be prematurely or permanently discontinued. Specific events that will result in stopping a participant's infusion schedule in either Part 1 or Part 2 of the study include:

- Failure to meet requirements established for safety assessment
- Pregnancy
- Development of a DLT at any time following MGD014 infusion
- Investigator discretion
- HIV RNA > 150 copies/mL on 2 consecutive determinations

If the PI (or designee) decides that a participant should be withdrawn from study treatment, the sponsor must be alerted within 24 hours. All participants who discontinue treatments should comply with protocol specified visits and follow-up as required by the protocol. The only exception to this requirement is when a participant withdraws consent for all study procedures or loses the ability to consent freely (i.e., is imprisoned or involuntarily incarcerated for the treatment of either a psychiatric or physical illness).

If a participant is withdrawn before completing the study, the reason for withdrawal must be documented appropriately in the study documents.

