9.3 Screening Period

Screening evaluations will be performed within 8 weeks (56 days) prior to study drug administration on Day 0 unless otherwise specified. At the 1st screening visit, participants will screen for the study. Only those participants who meet all eligibility criteria specified in [Section 5.1](#) Inclusion Criteria and [Section 5.2](#) Exclusion Criteria will be enrolled. A unique PID will be assigned during the screening visit. Participants who had previously completed Part 1 and are being considered for Part 2 will maintain the same PID and will be assigned a new study-specific identifier (SID).

Participants who are unable to meet protocol defined eligibility criteria at the Screening Visit (Step 1, Visit 1) may be eligible to re-screen again at the PI (or designee)'s discretion. In such cases, the same PID will be used. If a screen failure or the failure to enroll is due to the inability to meet one of the laboratory parameters (hematology, chemistry, HIV RNA, or CD4 T cell count), a laboratory retest of the failed criteria may be performed one time only. If the repeat value is within eligibility requirements, the participant can enroll on the study.

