17 Pre-MGD014 Infusion Medications (Diphenhydramine or equivalent H1-antihistamine and Acetaminophen) and other medications administered for hypersensitivity Anaphylactic Reaction:

- a. Diphenhydramine (IV) or equivalent H1-antihistamine and the Acetaminophen (oral) administered by licensed study staff.
- b. Administration of medications for treatment of adverse reactions to the MGD014 will follow hospital policy and the UNC HIV Cure Center SOP entitled “DART Infusion Guidelines and Emergency Management Plan”.

18 Post-Infusion Assessment: Participants provided with instructions to contact study staff about any reactions that occur after receipt of MGD014. Part 1 participants will return to the clinic on Days 1 and 2. Part 2 participants will return for Day 3 assessment and for post-infusion Day 14 and Day 28 to be contacted approximately 2 to 3 days after the study drug administration to inquire about reactions or any potential treatment emergent adverse events (TEAEs). Infusion reactions graded per the DAIDS Toxicity Table.

19 Chemistry: Na, K, Cl, bicarbonate, BUN, creatinine, glucose, Ca, total protein, AST, ALT, alkaline phosphatase, total bilirubin, and Mg. Indirect bilirubin required if participant on atazanavir. Clinical labs scheduled for the day of infusion (this is inclusive of CBC) can be obtained within 7 days of infusion.

20 Pregnancy test: Serum pregnancy test done on all women at screening. Urine pregnancy test/POCT done on all women at or within 72 hours of each infusion. Test results must be negative, documented and reviewed by study PI or designee prior to each infusion.

21 For ADA, PK, PD, RO, Serum Cytokine, and T Cell Phenotype measurements, please refer to [Appendix 2](#) for detailed schedule.

22 CBC done for leukapheresis procedure only.

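### Part 2 schedules no HIV-1 RNA test between screening and Day 77, so the viral-load stop and continue rules have no scheduled result to act on before the Day 14 or Day 28 infusion

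*Protocol*

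**What the plan says.** Protocol 5.3 lists events that end a participant's "infusion schedule in either Part 1 or Part 2 of the study include", and one of them is "HIV RNA > 150 copies/mL on 2 consecutive determinations". The rule is mandatory and names both parts.

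Protocol 9.11 takes over once a post-infusion viral load reaches 50 copies/mL. It asks for an adherence check and a repeat in 1 to 4 weeks. From 150 copies/mL upward, "the participant may continue with study treatment if repeat testing is < 100 copies/mL within 4 weeks and < 50 copies/mL within 12 weeks". It also says "HIV RNA will be repeated every 2 weeks, or sooner as clinically indicated, until < 50 copies/mL".

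For specimen timing, 9.11 points to Appendix 1. In the Part 2 table the HIV-1 RNA row is marked at Visit 1 (screening) and Visit 11 (Day 77) only, and the infusion row at Days 0, 14 and 28. The laboratory work marked on infusion days includes CBC and a chemistry panel, but not HIV RNA.

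Inclusion criterion 9 (5.1) requires a screening value below 50 copies/mL. On timing, 9.3 says "Screening evaluations will be performed within 8 weeks (56 days) prior to study drug administration on Day 0 unless otherwise specified".

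**The concern.** Part 1 gives one infusion, so as a control on dosing the 5.3 rule matters only in Part 2, at the second and third infusions. The repeats in 9.11 are reactive: they follow a first raised result and do not supply it. With nothing scheduled between screening and Day 77, a loss of suppression after Day 0 would reach the Day 14 and Day 28 dosing decisions only through reported missed ART doses or through a test that the protocol does not schedule. The monthly safety committee report (14.9) covers virologic failures, but Part 2 has no scheduled post-infusion value to feed it until Day 77.

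Two smaller wording points belong with this. The rules use different cut-offs (above 150 in 5.3; 150 or more in 9.11). The 12-week limb of 9.11 also runs well past the last infusion, although it is written as a condition for continuing treatment.

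**Working it through.** No sample size, power or error rate is involved. The check sets test days against infusion days in Appendix 1, Part 2.

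**Inputs**
- Infusions: Days 0, 14 and 28, with a window of ±1 day on Days 14 and 28.
- Standard HIV-1 RNA: screening and Day 77 (±3 days).
- Screening: at most 56 days before Day 0 (9.3); value below 50 (5.1, criterion 9).
- Stop rule: two consecutive values above 150 (5.3).

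**Step 1: scheduled results available at each infusion (nominal days)**

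| Infusion | Scheduled post-infusion HIV RNA results so far | Maximum age of last scheduled result |
|---|---|---|
| Day 0 | not applicable; screening value applies | 56 days |
| Day 14 | 0 | 56 + 14 = 70 days |
| Day 28 | 0 | 56 + 28 = 84 days |

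The longest gap between the two scheduled tests is 56 + 77 = 133 days.

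**Step 2: delay after dosing.** The first scheduled post-dose result comes 77 − 28 = 49 days after the last infusion. With visit windows the range is (77 − 3) − (28 + 1) = 45 to (77 + 3) − (28 − 1) = 53 days. A participant who stops early has the end-of-study visit 30 days after the last dose, which is also after dosing.

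**Step 3: can 5.3 be met before the last infusion on scheduled data?** It needs two values above 150. The screening value must be below 50, so it cannot be one of them, and there are no others before Day 28: 0 of the 2 needed.

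**Step 4: is the single copy assay a substitute?** In Part 2 it is drawn at enrollment, Day 1, Day 42 and Day 77. It is not drawn on Day 14 or Day 28, it is stored and shipped in batch (9.16), and neither rule refers to it.

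**Step 5: the 12-week limb.** If counted from Day 0, the earliest start, it expires on Day 12 × 7 = 84. That is 84 − 28 = 56 days after the last infusion and 84 − 77 = 7 days after the end-of-study visit. It cannot fail in time to affect a dose.

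**Step 6: after the proposed change.** Draws in the 7-day window fall on Days 7–14 and Days 21–28. That gives one post-infusion result before the Day 14 infusion and two before Day 28. The two draws are 21 − 14 = 7 to 28 − 7 = 21 days apart, so the second falls inside the 1-to-4-week repeat interval of 9.11.

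**The case against.** The best defence is that 5.3 and 9.11 are contingency rules. They act on any result, including a routine-care or for-cause test, and nothing in them promises a scheduled one. Participants enter after 24 months of continuous ART with documented suppression, dosing spans only 28 days, adherence is reviewed at every visit with continuation depending on it (9.7), and the safety committee sees ART interruptions monthly (14.9). Most of this stands, and it lowers the likely consequence. It does not close the gap: none of these safeguards measures viral load, and 5.3 is written on viral load.

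A reader might go further in four ways that the documents do not support.

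- **That the stop rule can never be met under the protocol.** A raised Day 77 value would set off the 9.11 repeats, which could produce two values above 150. The gap concerns the Day 14 and Day 28 infusions only.
- **That the ages should be 14 days longer**, because routine-care labs "completed within the 14 days preceding the screening visit can be used to qualify the participant upon approval by the study PI or designee". Section 9.3 limits screening evaluations to 56 days before Day 0, and that limit can be read as covering a routine-care lab used in their place. The figures above therefore stop at 56 days before Day 0.
- **That dosing a viremic participant has been shown to be unsafe.** No document ties 150 copies/mL to toxicity, and 2.4.3 reports no infusion reaction or cytokine release syndrome through Cohort 8. Section 2.4.1 considers the case of stopped ART and reports no in vitro cytokine release at up to 1000 ng/mL with cells from untreated viremic donors. It does report release at higher target-cell frequencies, so it does not settle the matter either way.
- **That 5.3 and 9.11 contradict each other.** One is mandatory and the other permissive, so they can be applied together.

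**Conclusion.** The point holds in a limited form. During Part 2 dosing, a stated participant-level stop rule and its companion continue rule have no scheduled post-infusion result to work on: none before Day 14 and none before Day 28. An unscheduled or routine-care test could still trigger either.

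The conclusion rests on three assumptions: the HIV-1 RNA row of the Part 2 table has been read correctly, visits fall on nominal days (the 70 and 84 days become 71 and 85 if an infusion uses its extra day), and screening takes the full 56 days allowed. On the first, the row has the same two marks as the CD4/CD8 and physical examination rows, and fuller rows such as CBC and infusion line up with the visit header, so a misread column is unlikely.

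Reach is up to 6 participants. The documents give no frequency of viremia at or above 150 copies/mL, so none is claimed, and no planned analysis changes. This is an inexpensive alignment of rule and schedule, not a flaw in the study's conclusions.

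**What to change.** 1. Add standard HIV-1 RNA to Appendix 1, Part 2, before the Day 14 and Day 28 infusions. The window already exists: "Safety laboratory tests can be performed up to 7 days prior to the infusion and must be reviewed before study drug administration", and Appendix 1 footnote 19 repeats the 7 days. The result should be reviewed before dosing. Then 9.11 can act at both infusions and 5.3 can act at Day 28.
2. Use one threshold, either above 150 or 150 and above, in both 5.3 and 9.11.
3. Reword the 12-week limb of 9.11 as follow-up of viremia, not a condition for further infusions.

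If the sponsor considers viral load unnecessary for dosing decisions in Part 2, the alternative is to say so and revise 5.3.

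**Cost.** A protocol amendment, 2 × 6 = 12 routine tests plus any repeats, and possibly a separate draw a few days before each of the two infusions if results are not available the same day, because Part 2 has no Day 7 or Day 21 visit.

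**Left to the sponsor.** Whether a single value of 150 or more should hold the next infusion. That would be a new rule with a real trade-off: the Day 14 and Day 28 windows are ±1 day, so waiting for a repeat could delay or lose a dose and shift the fixed-day PK and ADA samples. If a hold is adopted, the protocol should say whether the dose is given late or omitted.

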9.12 Central Laboratory Assays

Study specific safety and research samples will be collected at the research visit. Safety and clinically relevant assays will be performed at UNC McLendon Laboratories or LabCorp. Research assays will be processed and stored in associated research laboratories. Additional details on collection, processing, storage, and shipping of samples will be provided in the Study Specific Laboratory Manual.

9.13 Pharmacokinetics

Blood samples for MGD014 PK and ADA will be collected at the time points shown in [Appendix 1](#) and [Appendix 2](#). Further details of blood collection and processing will be provided in the Study Specific Laboratory Manual. Actual collection date and time must be recorded in the source documents.

9.14 Immunogenicity

Blood samples will be collected from the participant's arm contralateral to the site of IV infusion. If an indwelling catheter is used, the fluid in the indwelling catheter will be removed and discarded prior to the collection of blood sample for ADA assessment.

9.15 Pharmacodynamics

Appendix 1 and **Appendix 2** lists the sampling schedule to be followed for the assessment of the PD activity of MGD014. Further details of blood collection and processing will be provided in the Study Specific Laboratory Manual. Actual collection times must be recorded in the source documents.

9.16 Sample Collection, Storage, and Shipping

All blood samples acquired for PK and ADA described in **Section 10** will be processed at the UNC CFAR HIV/STD Laboratory Core (CHSLC) and shipped to MacroGenics for analysis.

All blood samples acquired for serum cytokine assays described in **Section 10.3.2** will be processed at CHSLC and shipped to Duke University for analysis.

Samples for RO, T cell phenotype, resting CD4 T Cell infection, and exploratory research assays (**Sections 10.3.1, 10.3.3, and 11.1.1**, respectively) will remain at UNC for processing and storage.

Samples for Plasma HIV-1 RNA SCA assays described in **Section 11.1.2** will be processed at UNC CHSLC, stored, and shipped in batch to National Cancer Institute (NCI) for analysis.

Details on laboratory specimen processing, storage, and shipping will be provided in the Study Specific Laboratory Manual.

9.17 Electrocardiography Monitoring

Twelve-lead ECGs will be obtained according to **Appendix 1** in order to evaluate the potential cardiac effects of MGD014, including QT interval. There are no requirements for fasting and no restrictions for fluid and food intake by the participants during this study. ECGs will be obtained as per **Appendix 1**.

9.18 End of Study Visit

End of study visit occurs after the last dose of study drug. See **Appendix 1**, Time and Events Schedule.

10 ASSESSMENT OF PHARMACOKINETICS AND PHARMACODYNAMICS

10.1 Pharmacokinetics Assessments

Serum concentrations of MGD014 will be monitored. Single and multiple dose PK parameters of C_{max} , time to maximal concentration (T_{max}), area under the concentration-time curve for a dosing interval (AUC_{tau}), trough concentration (C_{trough}), CL, V_{ss} , and terminal half-life ($t_{1/2}$) will be derived from serum concentration versus time data. Population PK analyses may be conducted using data from this study alone or combined with data from other studies.

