Study Design:

[figure not shown]
This is a Phase 1, open-label single-center study of MGD014 in PLWH on ART. Eligible participants will be maintained on ART and receive either one infusion (Part 1) or an IV infusion once every 2 weeks (Q2W) for a total of three infusions of MGD014 for 4 weeks (Part 2).

Part 1: Single Ascending Dose. Part 1 is a single ascending dose study with a 1+3 design for the first 2 dose cohorts, and a 3+3 design with staggered accrual for the 6 higher dose cohorts, with an aim of determining the safety, PK, and pharmacodynamics (PD) of ascending doses up to either the Optimal Biologic Dose (OBD) or the maximum administered dose (MAD).

Note: Cohort X represents any cohort number

Part 2: Multi-dose Expansion Cohort. Part 2 is a multi-dose expansion cohort with MGD014 300 mcg/kg administered IV once every 2 weeks (Q2W) for a total of three doses, as determined in Part 1 (which is equal to the MAD).

(a) Screening, eligibility and optional baseline leukapheresis (b) optional leukapheresis post-treatment for frequency of persistent infection of resting CD4 T cells.

Abbreviations: ADA = anti-drug antibody; ART = antiretroviral therapy; Leuk = leukapheresis; PK = pharmacokinetics; QVOA = quantitative viral outgrowth assay.

Main Criteria for Inclusion/Exclusion:

PLWH (18 to 65 years old) on ART with plasma HIV RNA < 50 copies/mL for 24 months prior to enrollment.

Test Product and Mode of Administration:

MGD014 will be supplied by MacroGenics, and administered via 2-hour infusions, a single IV infusion in Part 1, or IV infusion once every 2 weeks for 3 infusions over 4 weeks in Part 2.

Duration of Treatment and Study Duration:

The overall study duration will be approximately 24 months. For each individual participant, study duration will be approximately 10 weeks (Part 1) or 20 weeks (Part 2).

Treatment Schedule and Procedures:

See [Appendix 1](#).

Criteria for Evaluation:

Safety Assessments

Safety assessments will be based on medical review of adverse event (AE) reports, the results of vital sign (VS) measurements, electrocardiograms (ECGs), physical examinations, and clinical laboratory tests. The incidence of AEs will be tabulated and regularly reviewed for potential significance and clinical importance.

PK Assessments

- Single-dose and multiple-dose PK parameters for MGD014 may be derived from MGD014 serum concentration versus time data using non-compartmental analysis.

Immunogenicity (ADA) Assessments

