All animals were exposed to the test article after each administration of MGD014. Maximum serum concentration (C_{max}) and area under the curve (AUC) extrapolated up to infinity (AUC_{inf}) increased proportionally with increasing dose of MGD014. Based on the serum concentration profiles at the end of the first weekly dose, there were no significant differences between gender, therefore, male and female animals were grouped for subsequent analyses. Based on the overlapping dose normalized mean serum concentration profiles of the first week for all 3 doses and no significant difference between the total body clearance (CL) and steady-state volume of distribution (V_{ss}) among all 3 doses, MGD014 PK was determined to be linear across the dose range evaluated (0.1-10 mg/kg). By noncompartmental analysis (NCA), mean C_{max} after the first dose was 2, 19, and 180 μ g/mL for dose levels of 0.1, 1, and 10 mg/kg, respectively, consistent with the analysis by two-compartment modeling. By NCA, mean AUC_{inf} after the first dose was 74, 769, and 7255 $hr \cdot \mu$ g/mL for dose levels of 0.1, 1, and 10 mg/kg, respectively, consistent with the analysis by two-compartment modeling. Mean CL by NCA or two-compartment modeling of data after the first dose of MGD014 across all groups were consistent with each other at 1.38 or 1.4 mL/hr/kg, respectively, substantially lower than the glomerular filtration rate of cynomolgus monkeys, as would be expected for a protein of this size (111.8 kDa). Mean V_{ss} by NCA after the first dose of MGD014 across all doses was 141 mL/kg and by two-compartment modeling was 152 mL/kg, or about 3-fold larger than the plasma space (~45 mL/kg), but less than the extracellular space (~200 mL/kg) of cynomolgus monkeys. This indicates some extravasation into the extracellular space. Average mean residence time (MRT) after the first dose of MGD014 was 105 hours (4.4 days) by NCA and 117 hours (4.9 days) by two-compartment modeling. By simulation of 6 weekly doses using two-compartment modeling with PK parameters derived

from the first cycle of data, accumulation by a factor of 1.29 would be expected assuming PK parameters remained constant.

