Anti-drug antibodies (ADA) were confirmed in 10 out of 30 animals that received administration of MGD014. Of these, ADA was first detected in 4 animals during the dosing period (between Days 29 and 36) and in 6 animals during the recovery period (between Days 50 and 91). Although ADA were detected in 10 animals, no obvious changes in the PK profile were observed in these animals except for one animal from the 10 mg/kg dose group.

There were no noteworthy MGD014-related increases in serum concentrations of cytokines (IFN- γ , IL-2, IL-4, IL-5, IL-10, or TNF- α).

There also were no noteworthy MGD014-related changes in the frequencies of circulating CD4 and CD8 T cells, nor in the frequencies of CD4 and CD8 T cells expressing markers of activation or exhaustion (CD25, CD69, PD-1, TIM-3), as determined by flow cytometry. Assessment of MGD014 binding to CD4 and CD8 T cells demonstrated that binding to CD3 was 1-2% of maximal at 0.1 mg/kg, ~30% of maximal at 1 mg/kg, and maximal at 10 mg/kg, when measured at 24-hours post-infusion. Binding to CD3 was transient and nearly completely reversed for the low- and mid-dose groups and ~50% reversed for the high-dose group by 7-days post-infusion.

Based on these results, the no-observed-adverse-effect level (NOAEL) was considered to be 10 mg/kg/dose, which correlated to C_{max} of 180 μ g/mL and AUC_{last} of 5604 hr• μ g/mL.

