2.4.4 Every 2 Week Administration

For the multi-dose expansion cohort in Part 2, MGD014 at 300 mcg/kg will be administered IV Q2W for a total of three doses over 4 weeks. The Q2W administration of MGD014 is supported by the repeat-dose toxicology study in cynomolgus monkeys (Study 20093423) in which MGD014 was administered weekly for 6 weeks by 2-hour IV infusions. Simulations based on the allometric modeling of the cynomolgus monkey PK data predicts that the concentration profiles in human participants will reach steady-state between the third and fourth dosing intervals and that the accumulation factor for exposure following the last (sixth) dose will be 1.84.

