Note: Actual start and end of infusion times, PK, and ADA sample collection times will be recorded on the source documents. All sample time points are hours after EOI, unless otherwise specified. Samples required at EOI can be drawn up to 5 minutes before the infusion is complete, post EOI samples can be drawn +/- 5 minutes; duration of infusion = 120 minutes. 24 - and 48-hour samples will be drawn on Day 1 and 2 respectively.

Abbreviations: ADA = Anti-drug antibody; EOI = end of infusion; PK = Pharmacokinetic.

PART 2 Pharmacokinetics, Immunogenicity, and Pharmacodynamic Biomarkers Blood Sampling Schedule for MGD014						
MGD014 Dosing	Treatment Day	PK ^a Sampling Time (Hours)	ADA Sampling Time (Hours)	Receptor Occupancy ^b (Hours)	Serum Cytokines ^c (Hours)	T cell Phenotype (Hours)
X	0	0 ^d (Pre-infusion)		0 ^d (Pre-infusion)	0 ^d (Pre-infusion)	0 ^d (Pre-infusion)
	0	EOI				
	0	1 (post EOI)				
	0	4 (post EOI)		4 (post EOI)	4 (post EOI)	4 (post EOI)
	1	24 +/- 5 hours (post EOI)		24 +/- 5 hours (post EOI)	24 +/- 5 hours (post EOI)	24 +/- 5 hours (post EOI)
	3	72 +/- 5 hours (post EOI)			72 +/- 5 hours (post EOI)	
X	14	0 (Pre-infusion)	0 (Pre-infusion)	0 (Pre-infusion)		0 (Pre-infusion)
	14	EOI		4 (post EOI)	4 (post EOI)	4 (post EOI)
X	28	0 (Pre-infusion)	0 (Pre-infusion)	0 (Pre-infusion)		0 (Pre-infusion)
	28	EOI		4 (post EOI)	4 (post EOI)	4 (post EOI)
	42	1008 hours +/- 1 day				
	77 (EOS visit)	1848 hours +/- 3 days	X	X		X

- a Do not collect PK samples from infusion port. Obtain PK samples as follows: Pre-infusion: Before start of infusion on visit day (dosing day) or day before. When collecting multiple samples, collect the PK sample first.
- b If at any time in Step 3 RO reaches below the limit of detection, at the discretion of the PI or designee, further measurement of RO may be deemed unnecessary.
- c Additional samples may be obtained selectively at additional time points in participants who experience signs and symptoms of cytokine release.
- d All pre-dose PK, ADA, Receptor Occupancy including T-cell binding, cytokines, and T-cell Phenotype samples will be collected prior to start of MGD014 infusion; the start of MGD014 infusion is designated as time = 0 hour.

Abbreviations: ADA = Anti-drug antibody; EOI = end of infusion; PK = Pharmacokinetic.

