4.10 Pharmacokinetic Endpoints and Analyses

Geometric means and percent coefficients of variation may be reported for C_{max} , AUC, and C_{trough} ; arithmetic means and standard deviations may be reported for $t_{1/2}$, CL, and V_{ss} ; and medians, minimum, and maximum will be reported for T_{max} .

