4.12 Immunogenicity Endpoints and Analyses

The proportion of participants who are negative for MGD014 ADA at baseline and become positive in this assay, the proportion of participants who are negative at baseline and remain negative, and those who have positive ADA at baseline that increases or decreases in titer over the course of treatment will be summarized. Positive samples will be evaluated for neutralizing capacity and the incidence of neutralizing antibodies will also be summarized. The impact of immunogenicity on safety, PK, and PD will be summarized and explored graphically.

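### Multiple-dose AUCtau, CL and Vss are to be derived, but PK sampling after doses 2 and 3 of Part 2 is too sparse for NCA, the one method named for deriving them

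*Protocol*

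**What the plan says.** **Commitment and method.** Protocol 10.1 lists Cmax, Tmax, AUCtau, Ctrough, CL, Vss and terminal half-life, single and multiple dose, and says they "will be derived from serum concentration versus time data. Population PK analyses may be conducted using data from this study alone" or combined with other studies. It does not say for which dose each parameter is derived. The synopsis says single- and multiple-dose parameters "may be derived from MGD014 serum concentration versus time data using non-compartmental analysis". SAP 4.10 covers summary statistics only; for half-life, CL and Vss, "arithmetic means and standard deviations may be reported for" them.

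**Sampling.** Protocol Appendix 2, Part 2 sets these PK samples:

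| Dose | PK samples in the 14 days after the dose | Later |
|---|---|---|
| 1 (Day 0) | EOI, 1, 4, 24 and 72 h, Day 14 pre-infusion | – |
| 2 (Day 14) | EOI, Day 28 pre-infusion | – |
| 3 (Day 28) | EOI, Day 42 ("1008 hours +/- 1 day") | Day 77 |

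**Accumulation.** Protocol 2.4.4, on the every-2-week (Q2W) schedule of three doses, says that "the accumulation factor for exposure following the last (sixth) dose will be 1.84". For monkeys on six weekly doses, 2.2.2 says "accumulation by a factor of 1.29 would be expected assuming PK parameters remained constant".

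**The concern.** With one sample at the peak and the next 14 days later, NCA draws a single segment across the whole distribution phase. Concentrations fall quickly at first and slowly afterwards, so that segment lies above the true curve and AUCtau comes out too high. CL comes out too low, and Vss inherits the error.

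Dose 1 has a full profile and is nearly free of this bias. The error therefore does not cancel in a dose 3/dose 1 ratio, and more participants would not remove it. It would look like accumulation with falling clearance. PK is a secondary objective, and Part 2 is its only multiple-dose source. For Part 2, SAP 4.12 also says: "The impact of immunogenicity on safety, PK, and PD will be summarized and explored graphically".

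**Working it through.** **Inputs, all from the Protocol.** Cmax 5151.4 and 7-day concentration 802.6 ng/mL at 300 µg/kg (Table 1); half-life 8 days (4.5); AUC 83 ng/mL·h at 0.1 µg/kg (2.4.1); 2-hour infusion. Per µg/kg these are 17.17, 2.675 and 830.

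**Assumption.** No interval is stated for the 83; I read it as 0–168 h. Section 2.4.1 compares it with the monkey AUClast of the first weekly cycle (5,604,000/83 = 67,518, stated as more than 67,000-fold). Longer intervals do not fit: with an 8-day half-life and the 7-day value, the terminal phase alone gives about 1,354 to infinity and about 950 over 0–336 h, both above 830.

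**Model.** Two compartments, infusion time T = 2 h. For t ≥ T, C(t) = Σ K/(kT)·(e^(kT) − 1)·e^(−kt) over (K, k) = (A, α) and (B, β), with β = ln 2/192 = 0.00361/h. Matching C(2) = 17.17, C(168) = 2.675 and AUC(0–168) = 830 gives A = 13.06, α = 0.0602/h (distribution half-life about 11.5 h) and B = 4.89.

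**Reproducing the plan's figures.** By superposition, accumulation at dose n is AUC(0–nτ)/AUC(0–τ) after a single dose.
- Monkey, weekly: AUCinf/AUClast = 7255/5604 = 1.29, as stated. The protocol's factor thus behaves as a weekly AUC ratio.
- Human, six weekly doses: AUC(0–1008)/AUC(0–168) = 1535/830 = 1.85, against 1.84 printed (1.84 to 1.85 over the rounding of 83).
- Human, three Q2W doses: AUC(0–1008)/AUC(0–336) = 1535/1167 = 1.32.

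**NCA after dose 3 at 300 µg/kg.** Modelled concentrations: pre-dose 568, EOI 5,715, 14 days 606 ng/mL. True AUCtau is about 460,500 ng·h/mL.
- Infusion segment: (568 + 5715)/2 × 2 = 6,283.
- Linear: 6,283 + (5715 + 606)/2 × 334 ≈ 1,061,900; divided by the true value, 2.31.
- Log: 6,283 + (5715 − 606)/ln(5715/606) × 334 ≈ 766,700; divided by the true value, 1.66.
- Dose 2 by the same steps: about 2.4 and 1.7.

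**NCA after dose 1.** Samples at 2, 3, 6, 26, 74 and 336 h give about 361,500 (log) and 382,000 (linear). Against a true 350,100 that is 1.03 and 1.09.

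**Consequences.**
- Dose 3/dose 1 AUC ratio: true 460,500/350,100 = 1.32; log 766,700/361,500 = 2.12; linear 1,061,900/382,000 = 2.78.
- CL as dose/AUCtau: 300,000/460,500 = 0.65 mL/h/kg with the true AUCtau; 0.39 (log, 40% low); 0.28 (linear, 57% low).
- Sampled directly: Ctrough ratio 606.3/437.5 = 1.39; Cmax ratio 5715/5151 = 1.11.

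**Sensitivity, dose-3 AUCtau over true, log to linear.**
- Half-life 7 to 9 days: log 1.66 throughout, linear 2.37 to 2.25. The true Q2W accumulation is then 1.26 to 1.37.
- Distribution half-life varied, dropping the match to 83: 6 h, about 1.8 to 2.5; 24 h, about 1.5 to 2.1; 48 h, about 1.2 to 1.9.

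**Half-life after dose 3.** The Day 42–77 slope returns 8.0 days in the model, but from two points. The modelled Day 77 level is about 29 ng/mL, and no assay limit is given.

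**The case against.** The strongest reply is that the error is hypothetical. Only 10.1 says the parameters will be derived; the synopsis and SAP 4.10 both use may. A rich first-dose profile followed by sparse samples suits the population PK option in 10.1. In the monkey study the sponsor used NCA on first-dose data and obtained accumulation by two-compartment simulation. SAP Section 5 defers specifications to a programming plan that is not among these documents. The sizes rest on preclinical projections, and Part 1 has reached 300 µg/kg, so human profiles can replace them.

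Most of this stands. A reader might infer that the sponsor has committed to NCA after doses 2 and 3; the documents do not say so. What remains is that NCA is the only method named for deriving these parameters, nothing restricts it to dose 1, and the choice is left open until data are in hand.

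Three further inferences go too far:
- *A clearance change from anti-drug antibodies (ADA) would be hidden.* NCA AUC and CL could mislead, but other planned outputs would show it. If clearance doubled from dose 2, the Ctrough ratio would fall from 1.39 to 0.35, and the Day 42–77 half-life would shorten. In monkeys ADA first appeared on Day 29 or later, and only one of 10 positive animals had an obvious PK change. ADA-positive screenees are excluded from Part 2.
- *Half-life will be wrong.* That requires putting the EOI peak into the slope, and 10.1 asks for terminal half-life.
- *1.84 is a miscalculation.* It reproduces for six weekly doses, overstates Q2W accumulation and feeds no analysis.

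**Conclusion.** The point holds as under-specification with a predictable bias if the named method is followed. On the protocol's projections, NCA would overstate dose-3 AUCtau about 1.7- to 2.3-fold, against 1.03 to 1.09 for dose 1. This rests on a two-compartment shape, an 8-day half-life, the 0–7 day reading of the 83, and allometric projection from monkeys. The direction is robust over the ranges tried; the size is not settled until Part 1 data show the human distribution phase. Vss was not quantified separately.

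Cmax and Ctrough are adequately covered. Half-life after dose 3 is obtainable, but from two points. Severity is minor to a mild recommendation: the objective is secondary and descriptive, and the primary safety objective is untouched. The 1.84 label and the wording in 2.4.2, which explains a 7-day trough by a 14-day dosing interval, are editorial.

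**What to change.** Add to Protocol 10.1 and SAP 4.10:

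> After doses 2 and 3 of Part 2, NCA is limited to Cmax and Ctrough, and NCA accumulation ratios use these only. AUCtau, CL and Vss for these doses are reported only if derived from a compartmental or population PK model, and otherwise are not reported. Half-life after dose 3 uses the Day 42–77 slope, labelled as two-point, or the model.

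If a model is used, it should not force one clearance across doses when the effect of ADA is examined, since that would make a change invisible. The model structure is otherwise for the sponsor to choose. With up to 6 participants and two or three samples per later dose, prescribing dose- or ADA-specific clearance would ask more than the data can bear.

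Editorial: in 2.4.4, label 1.84 as a projection for six weekly doses and add the sponsor's own value for three Q2W doses (about 1.3 on these projections). In 2.4.2, correct the reason given for showing a 7-day trough.

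Cost: text edits, plus model development only if the sponsor wants the later-dose AUCtau, CL and Vss. The downside is that these become model-dependent or are not reported. No change to dose, interval or sampling is implied.
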